APPENDIX 4: List of Inclusion and Exclusion Criteria which has Impact on Efficacy Analysis

Criteria No.	Criteria
Inclusion Criteria	#2 Patient has histologically confirmed CD20+ FL grade 1 to 3a according to the World Health Organization 2008 classification (Jaffe et al 2009); biopsy within 6 months before the first administration of the study drug.
	#3 Patient has at least 1 measurable tumour mass in 2 dimensions, and the mass must be: 
 • Nodal lesion >15 mm in the longest dimension; or • Nodal lesion >10 mm to ≤15 mm in the longest dimension and >10 mm in the shortest dimension; or • Extranodal lesion with both long and short dimensions ≥10 mm.
	#4 Patient has Ann Arbor stage II, III, or IV disease.
	#5 Patient has low tumour burden, defined as based on Groupe d'Etudes des Lymphomes Folliculaires (GELF) criteria: 
 • No B symptoms, • LDH < upper limit of normal (ULN), • Largest nodal or extra mass < 7 cm, • < 3 nodal sites with a diameter ≥3 cm, • No significant serous effusions detectable clinically or on CT (small, clinically non-evident effusions on CT scan are not deemed significant), • Spleen ≤16 cm by CT, and • No clinical organ failure or organ compression (e.g. ureteric obstruction)

	#6	Patient has an Eastern Cooperative Oncology Group (ECOG) performance status of 0 to 1 (Oken et al 1982).
Exclusion Criteria	#1	Patient has received rituximab (or a rituximab proposed biosimilar product).
	#3	Patient has evidence of histological transformation to high-grade or diffuse large B-cell lymphoma.
	#4	Patient has known central nervous system involvement or any evidence of spinal cord compression by lymphoma.
	#5	
Patient has received previous treatment for NHL:
 
 • Previous treatment including chemotherapy, radiotherapy, immunotherapy, and/or surgery (except previous biopsy). • All doses of corticoid therapy for treatment of NHL. • Corticoid therapy within 4 weeks before the first administration of the study drug, with prednisone >20 mg per day (or equivalent doses of other steroid medications) for any purpose except NHL.
	#9	Patient has any malignancy other than NHL, except adequately treated squamous or basal cell carcinoma of the skin or cervical carcinoma in situ, within the 5 years before the first administration of the study drug.
	#10	Patient has a current or recent treatment (within 42 days before the first administration of the study drug or 5 times the half-life, whichever is longer, prior to screening) with any other investigational medicinal product or device.

APPENDIX 5: Rule of combining Preferred Terms

SOC	PT	Combined PT
Gastrointestinal disorders	Abdominal pain Abdominal pain lower Abdominal pain upper	Abdominal pain
Infections and infestations	Abscess oral Subcutaneous abscess	Abscess
Blood and lymphatic system disorders	Anaemia Iron deficiency anaemia	Anaemia
Psychiatric disorders	Anxiety Anxiety disorder Anxiety disorder due to a general medical condition	Anxiety
Musculoskeletal and connective tissue disorders	Arthritis reactive Arthritis	Arthritis
Infections and infestations	Bacterial vaginosis Vaginitis bacterial	Bacterial vaginosis
Infections and infestations	Asymptomatic bacteriuria Bacteriuria	Bacteriuria
Cardiac disorders	Bradycardia	Bradycardia

	Sinus bradycardia	
Cardiac disorders	Cardiac failure Cardiac failure chronic	Cardiac failure
General disorders and administration site conditions	Chest pain Non-cardiac chest pain	Chest pain
Hepatobiliary disorders	Bile duct stone Cholelithiasis	Cholelithiasis
Infections and infestations	Conjunctivitis Conjunctivitis bacterial	Conjunctivitis
Respiratory, thoracic and mediastinal disorders	Cough Productive cough	Cough
Skin and subcutaneous tissue disorders	Dermatitis Dermatitis allergic Dermatitis atopic Stasis dermatitis Dermatitis contact Seborrhoeic dermatitis Solar dermatitis	Dermatitis
Metabolism and nutrition disorders	Diabetes mellitus	Diabetes mellitus

	Type 2 diabetes mellitus Type 1 diabetes mellitus	
Skin and subcutaneous tissue disorders	Drug eruption Toxic skin eruption	Drug eruption
Skin and subcutaneous tissue disorders	Dyshidrotic eczema Eczema Eczema nummular	Eczema
Injury, poisoning and procedural complications	Ankle fracture Facial bone fracture Femur fracture Foot fracture Hand fracture Humerus fracture Lower limb fracture Lumbar vertebral fracture Rib fracture Tibia fracture Tooth fracture Ulna fracture	Fracture

	Upper limb fracture Wrist fracture Patella fracture	
Infections and infestations	Fungal infection Fungal skin infection Genital infection fungal Oral candidiasis Oral fungal infection Vulvovaginal candidiasis Balanitis candida Aspergillus infection Onychomycosis	Fungal infection
Nervous system disorders	Headache Tension headache	Headache
Infections and infestations	Helicobacter gastritis Helicobacter infection	Helicobacter infection
Infections and infestations	Herpes simplex Herpes zoster Oral herpes	Herpes virus infection

	Genital herpes simplex	
Metabolism and nutrition disorders	Glucose tolerance impaired Hyperglycaemia Impaired fasting glucose	Hyperglycaemia
Immune system disorders	Drug hypersensitivity Hypersensitivity	Hypersensitivity
General disorders and administration site conditions	Catheter site pain Injection site haematoma Injection site pain Puncture site pain	Injection site reaction
Injury, poisoning and procedural complications	Chest injury Cartilage injury Craniocerebral injury Concussion Contusion Eye contusion Fall Injury Limb injury	Injury

	
Meniscus injury
 
Skin injury
 
Tendon rupture
 
Wound
 
Bone contusion
 
Back injury
 
Ear injury
 
Limb crushing injury
 
Muscle injury
 
Muscle rupture
 
Radiation skin injury
 
Skin abrasion
 
Laceration
	
Musculoskeletal and connective tissue disorders	
Intervertebral disc disorder
 
Intervertebral disc protrusion
	Intervertebral disc disorder
Infections and infestations	
Bacterial infection
 
Localised infection
 
Pulpitis dental
 
Skin infection
	Localised infection

	
Tooth infection
 
Tonsillitis bacterial
 
Staphylococcal infection
 
Eczema infected
 
Nail infection
 
Infected dermal cyst
	
Infections and infestations	
Bronchiolitis
 
Bronchitis
 
Lower respiratory tract infection
 
Lung infection
 
Respiratory tract infection
 
Respiratory tract infection viral
	Lower respiratory tract infection
Nervous system disorders	
Neuropathy peripheral
 
Peripheral sensory neuropathy
 
Toxic neuropathy
	Neuropathy peripheral
General disorders and administration site conditions	
Face oedema
 
Generalised oedema
 
Localised oedema
 
Oedema peripheral
	Oedema

	Peripheral swelling Swelling	
Infections and infestations	Otitis externa Otitis media Otitis media acute Otosalpingitis	Otitis
Infections and infestations	Pneumocystis jirovecii pneumonia Atypical mycobacterial pneumonia Pneumonia	Pneumonia
Skin and subcutaneous tissue disorders	Pruritus Pruritus generalised Pruritus allergic	Pruritus
Skin and subcutaneous tissue disorders	Rash Rash erythematous Rash generalised Rash macular Rash maculo-papular Rash pruritic	Rash
Infections and infestations	Rhinitis	Rhinitis

	Viral rhinitis	
Infections and infestations	Acute sinusitis Sinusitis Sinusitis bacterial	Sinusitis
Gastrointestinal disorders	Mouth ulceration Stomatitis Aphthous ulcer	Stomatitis
Cardiac disorders	Sinus tachycardia Supraventricular tachycardia Tachycardia Ventricular tachycardia	Tachycardia
Infections and infestations	Body tinea Tinea capitis Tinea infection Tinea pedis	Tinea infection
Infections and infestations	Laryngitis Nasopharyngitis Pharyngitis Pharyngitis bacterial	Upper respiratory tract infection

	
Viral pharyngitis
 
Pharyngotonsillitis
 
Tonsillitis
 
Tracheitis
 
Tracheobronchitis
 
Sinobronchitis
 
Upper respiratory tract infection
 
Viral upper respiratory tract infection
 
Upper respiratory tract infection bacterial
	
Infections and infestations	
Cystitis
 
Urinary tract infection
 
Urethritis
	Urinary tract infection
Skin and subcutaneous tissue disorders	
Mechanical urticaria
 
Urticaria
	Urticaria
Vascular disorders	
Venous thrombosis
 
Venous thrombosis limb
 
Jugular vein thrombosis
	Venous thrombosis
Ear and labyrinth disorders	
Vertigo
 
Vertigo positional
	Vertigo

Infections and infestations	Gastrointestinal viral infection Gastroenteritis viral Gastroenteritis norovirus	Gastroenteritis viral
Nervous system disorders	Dizziness Dizziness postural	Dizziness
Nervous system disorders	Dysaesthesia Paraesthesia	Paraesthesia
Respiratory, thoracic and mediastinal disorders	Oropharyngeal pain Oropharyngeal discomfort	Oropharyngeal pain
Nervous system disorders	Anosmia Hyposmia	Anosmia
Gastrointestinal disorders	Intestinal polyp Large intestine polyp	Intestinal polyp
Hepatobiliary disorders	Cholecystitis Cholecystitis chronic	Cholecystitis
Musculoskeletal and connective tissue disorders	Tenosynovitis Tenosynovitis stenosans	Tenosynovitis
Psychiatric disorders	Depressed mood Depression	Depression

	Depressive symptom	
Renal and urinary disorders	Calculus ureteric Calculus urinary	Calculus ureteric

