13.1. Adverse Events

An adverse event (AE) is defined as any untoward medical occurrence in a patient enrolled (i.e., when the ‘Informed Consent’ page of eCRF is recorded) into the study regardless of its causal relationship to study drug.

A treatment-emergent AE (TEAE) is defined as any event not present before exposure to study treatment or any event already present that worsens in intensity or frequency after exposure to study treatment.

The MedDRA version 18.1 or later will be used to code all AEs. AEs will be graded for intensity according to CTCAE version 4.03.

All AEs occurring during the study will be listed by treatment group. Listings for AEs will include following information: Study period (Induction to MP1, MP2, and Follow-up); SOC, PT and verbatim term; start and stop date; duration (days from start date until stop date of an AE); frequency (intermittent, continuous); outcome (recovered/resolved, recovering/resolving, recovered/resolved with sequelae, not recovered/not resolved, fatal, unknown); any treatment required (no, yes with specified treatment); intensity (CTCAE grade 1 to 5); action taken by investigator (no action taken, dose decreased, dose interruption [or prolonged], permanently discontinued, dose delay); relationship to study drug (unrelated, possible, probable, definite); whether the event is serious (yes, no); and whether patient is terminated from the study due to AE

(yes, no).

In summaries, AEs will be considered to be related if the relationship is possible, probable or definite. If relationship or intensity is missing, it will be summarized separately under a missing category.

Combined PTs using [APPENDIX 5](#) will be summarized in AE tables. Listings will include PTs as coded without applying the PT combining rule.

Summaries related AEs will be presented in overall and by each study period (Induction to MP1, MP2 and Follow-up). Any AE having a start date on or after Induction Cycle 1 visit date and before Maintenance Cycle 7 visit date or Follow-up 1 visit date (in case a patient with discontinuation before Maintenance Cycle 7) will be included in the Induction to MP1 Period. Any AE having a start date on or after the Maintenance Cycle 7 visit date and before Follow-up 1 visit date will be included in the MP2 Period. Any serious adverse drug reaction (SADR) reported in the eCRF having a start date on or after the Follow-up 1 visit date and up to last Follow-up visit date will be included in the Follow-up Period.

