13.1.1. Incidence of Treatment-Emergent Adverse Events

Treatment-Emergent Adverse Events and TEAEs reported for at least 3% and 5% of patients in either treatment group will be summarized. For the Summary of TEAE reported for at least 3% and 5% of patients in either treatment group, it will be only presented with relationship to study drug.

All TEAEs will be flagged in the listing for AEs described in [Section 13.1](#).

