13.1.5. Treatment-Emergent Adverse Events of Special Interest

The following will be considered as AEs of special interest: infusion-related reactions (IRR), infections and progressive multifocal leukoencephalopathy (PML).

TEAEs of IRR will be determined if the information is recorded as IRR in the ‘Adverse Events’ page of the eCRF. TEAEs of infections will be determined if a SOC is ‘Infections and infestations’. Although PML is an AE of special interest, it is captured only by a PT ‘Progressive multifocal leukoencephalopathy’. Therefore, TEAEs of PML will be included in the summary of TEAEs instead of generating an additional table.

All TEAEs of IRR and infections will be listed separately including variables detailed in [Section 13.1](#). With variables detailed in [Section 13.1](#), the listing will include information recorded on the ‘Adverse Events’ and ‘Infusion related/Anaphylactic Reaction’ page of eCRF will be included: start/stop time of IRR; signs and symptoms; whether symptoms are experienced (no, yes with

specified intensity NCI CTCAE); the lowest blood pressure (BP) level after study drug exposure [mmHg] and date/time of BP assessment (if BP is decreased after study drug exposure); comments on IRR.

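### SAP Appendix 5 counts bacterial tonsillitis as a localised infection and unspecified respiratory infections as lower-tract, so some combined-PT rows in the AE tables would be mislabelled

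*SAP*

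**What the plan says.** Appendix 5 of the SAP is a look-up table that assigns coded PTs to combined PTs. Under SAP 13.1, the combined PTs "will be summarized in AE tables. Listings will include PTs as coded without applying the PT combining rule".

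The entries at issue all lie in the SOC *Infections and infestations*:

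- *Lower respiratory tract infection* holds six PTs: bronchiolitis, bronchitis, the row's own term, lung infection, *Respiratory tract infection* and "Respiratory tract infection viral".
- *Upper respiratory tract infection* holds 13 PTs, among them tonsillitis, pharyngotonsillitis, bacterial pharyngitis, tracheitis, "Tracheobronchitis" and sinobronchitis.
- *Localised infection* holds ten PTs. Several are skin, nail and dental terms; "Tonsillitis bacterial", *Bacterial infection* and "Staphylococcal infection" are also there.

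The SAP gives no rationale for the groups. SAP 13.1 tabulates treatment-emergent events, including those of special interest, by SOC and PT, and counts a patient once at each level. SAP 13.1.1 adds frequency tables: "TEAEs reported for at least 3% and 5% of patients in either treatment group will be summarized". SAP 13.1.5 lists infections among the events of special interest and identifies them by SOC.

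**The concern.** Merging similar PTs is ordinary practice. The difficulty is that some coded terms are sent to a row whose label says something the term does not say, or that the table contradicts elsewhere. A reader takes a row labelled as lower respiratory tract infection to count patients with a recorded lower-tract infection.

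Infection is an event of special interest here. Within its SOC, the PT rows are the only breakdown by type of infection that the SAP describes for the tables. If a label is wrong, the reader has to rebuild the row from patient listings. What is at stake is the accuracy of descriptive safety rows, not the similarity conclusion.

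**Working it through.** There is no stated figure to reproduce, so the check has three parts: compare the mappings with each other, trace which outputs use them, and gauge the scale.

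**1. Mappings compared within Appendix 5**

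| Coded term | Combined row | Comparator in the same table |
|---|---|---|
| Tonsillitis bacterial | Localised infection | Tonsillitis, pharyngotonsillitis and bacterial pharyngitis: upper respiratory |
| Respiratory tract infection; its viral form | Lower respiratory | None; the term names no level |
| Tracheobronchitis, sinobronchitis | Upper respiratory | Bronchitis: lower respiratory; tracheitis: upper respiratory |
| Bacterial infection, staphylococcal infection | Localised infection | None; the term names no site |

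The bacterial forms of pharyngitis, sinusitis, conjunctivitis and upper respiratory tract infection all stay with their site. Bacterial tonsillitis does not, so the first line is an internal inconsistency. In the second line, the label adds a level that the coded term lacks. The third line splits terms naming the bronchi across two rows, but each of the two terms spans two sites. The fourth is a looser labelling matter. A similar case outside infections is *Calculus urinary*, a general term counted under *Calculus ureteric*.

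**2. Which outputs move**

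Take four hypothetical patients: A with bronchitis, B with bacterial tonsillitis, C with *Respiratory tract infection*, and D with both tonsillitis and bacterial tonsillitis.

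| Row | Appendix 5 as written | After the two firm corrections |
|---|---|---|
| Lower respiratory | A, C = 2 | A = 1 |
| Upper respiratory | D = 1 | B, D = 2 |
| Localised | B, D = 2 | 0 |
| Level not specified | no such row | C = 1 |
| Patients in the SOC | 4 | 4 |

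PT rows change and the SOC count does not. Infections of special interest are selected by SOC, so that selection does not change either. Listings keep the coded PTs.

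**3. Scale in the frequency tables**

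Inputs: 87 per arm (SAP 5.2), or 250 / 2 = 125 per arm at the maximum in SAP 5.2; thresholds of 3% and 5% (SAP 13.1.1). The Safety population is assumed to equal the planned arm size. The minimum count is n × threshold, rounded up.

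| n per arm | 3% table | 5% table |
|---|---|---|
| 87 | 2.61, so 3 patients (3.45%; 2 would be 2.30%) | 4.35, so 5 patients (5.75%; 4 would be 4.60%) |
| 125 | 3.75, so 4 patients (3.2%; 3 would be 2.4%) | 6.25, so 7 patients (5.6%; 6 would be 4.8%) |

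Three patients coded only to an unspecified respiratory term in an arm of 87, or four in an arm of 125, would therefore list *Lower respiratory tract infection* in the 3% table with no lower-tract event on record. One patient moved between rows shifts a percentage by 1/87 = 1.15 points and can add or remove a row.

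**The case against.** The strongest reply is that the parts of the safety analysis that matter most are insulated. Infections of special interest are chosen by SOC and have their own listing, the coded terms stay in the listings, the rule is the same in both arms, and all treatment-emergent events are summarised whatever their frequency. All of that stands, and it limits the point to PT-level rows.

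A second reply is that the documents set no anatomical standard. *Localised infection* looks like a residual group, and fungal and herpes terms are grouped by organism across sites. This stands for tracheobronchitis and sinobronchitis, whose placement is arguable because tracheitis is also in the upper group. It largely stands for the bacterial and staphylococcal terms. It does not rescue bacterial tonsillitis, because other bacterial forms in the table follow their site. Nor does it supply a reason to call an unspecified infection lower-tract.

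A reader might also infer that adding the same unspecified events to both arms hides a real difference between them. The documents do not support that. Suppose true rates of 5% and 10%, with u points of unspecified infection added to each (assumed figures, no overlap). The difference is (10 + u) − (5 + u) = 5 points for every u. Only the ratio shrinks: 12/7 = 1.71, 15/10 = 1.50 and 18/13 = 1.38 for u = 2, 5 and 8. The AE tables report counts and percentages, and neither document plans an AE ratio or a between-arm AE test. The example also assumes that unspecified infections are never lower-tract and are equally common in both arms, which nothing in the documents establishes.

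**Conclusion.** The point holds in a limited form. Bacterial tonsillitis is mapped inconsistently with the rest of Appendix 5, and the two unspecified respiratory terms are given a level they do not state. Following the SAP as written would mislabel some combined-PT rows if such events occur.

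The size cannot be stated as a count, because the documents hold no event data. The minimum patient counts above show only that a few patients suffice to create a row, and they rest on the Safety population matching the planned arm sizes. It would go too far to say that the special-interest infection counts are wrong, that tracheobronchitis is definitely misplaced, or that the grouping biases the comparison of arms. This is a correction to safety presentation with no bearing on efficacy.

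**What to change.** Edit Appendix 5 as follows:

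- Move bacterial tonsillitis to the group that holds tonsillitis.
- Leave the two unspecified respiratory terms uncombined, or give them a row marked as level not specified.
- State one rule for bronchitis, tracheobronchitis and sinobronchitis, and apply it to all three.
- Optionally, leave the bacterial and staphylococcal infection terms uncombined, and relabel the *Calculus ureteric* row with the general term.

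Make the edit before the randomisation code is broken for the 1st CSR (SAP 5.3). If those tables already exist, show both versions so that the change cannot look data-driven. The cost is an edit to one look-up table, a re-run of the AE tables and a few more rows.

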 - Corticoid therapy within 4 weeks before the first administration of the study drug, with prednisone >20 mg per day (or equivalent doses of other steroid medications) for any purpose except NHL.
6. Patient has a severe infection, such as sepsis, abscesses, active tuberculosis (TB), or opportunistic infections.
7. Patient has a known infection with human immunodeficiency virus (HIV), hepatitis B, or hepatitis C (carriers of hepatitis B and hepatitis C are not permitted to enrol into the study).
8. Patient has New York Heart Association class III or IV heart failure, severe uncontrolled cardiac disease (unstable angina, clinically significant electrocardiogram [ECG] abnormalities), or myocardial infarction within the previous 6 months before the first administration of the study drug.
9. Patient has any malignancy other than NHL, except adequately treated squamous or basal cell carcinoma of the skin or cervical carcinoma in situ, within the 5 years before the first administration of the study drug.
10. Patient has a current or recent treatment (within 42 days before the first administration of the study drug or 5 times the half-life, whichever is longer, prior to screening) with any other investigational medicinal product or device.
11. Patient has uncontrolled diabetes mellitus, even after insulin treatment.
12. Patient is pregnant or lactating. Patients who are planning to be pregnant or to breastfeed before, during, or within 12 months after the last administration of the study drug are not permitted to enrol into the study.
13. Patient is taking a live, live-attenuated, or nonlive vaccine within 4 weeks before the first administration of the study drug.
14. Patient has evidence of any other coexisting disease or medical or psychological condition, metabolic dysfunction, unstable pulmonary condition, physical examination finding, or clinical laboratory finding giving reasonable suspicion of a disease or condition that contraindicates the use of an investigational product, or patient is high risk for treatment complications at the investigator's discretion.

Statistical Methods:

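### Appendix 5 folds Pneumocystis and atypical mycobacterial pneumonia, Aspergillus infection and ventricular tachycardia into broader rows, so no table described in the SAP shows them by arm

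*SAP*

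**What the plan says.** SAP 13.1 states that adverse event tables summarise the combined preferred terms (PTs) of Appendix 5. It then exempts the listings: "Listings will include PTs as coded without applying the PT combining rule". Neither 13.1 nor 13.1.1 to 13.1.5 makes an exception for any table.

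The Appendix 5 rows at issue are:

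- **Pneumonia:** "Pneumocystis jirovecii pneumonia Atypical mycobacterial pneumonia Pneumonia".
- **Fungal infection:** "Fungal infection Fungal skin infection Genital infection fungal Oral candidiasis Oral fungal infection Vulvovaginal candidiasis Balanitis candida Aspergillus infection Onychomycosis".
- **Tachycardia:** "Sinus tachycardia Supraventricular tachycardia Tachycardia Ventricular tachycardia".

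A fourth row, Herpes virus infection, includes "Herpes simplex Herpes zoster Oral herpes" and is a weaker case.

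SAP 13.1.5 names infusion-related reactions, infections and progressive multifocal leukoencephalopathy (PML) as events of special interest. Infections are identified by organ class. On listings, 13.1 says: "All AEs occurring during the study will be listed by treatment group".

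**The concern.** Comparing overall safety with Rituxan is a secondary objective (Protocol Synopsis; SAP 3.2), and infections are an event of special interest. The infection and serious event tables are where a reader looks for a difference between arms. In the three rows above, a clinically distinct and potentially serious diagnosis sits with broader or commoner ones, and the row label gives no sign of it.

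In a trial meant to show similarity, this works in one direction. A small imbalance in a rare event, added to background events that are balanced between arms, makes the row look more alike than the rare event alone would. A reader of the tables has no prompt to go to the listings and check.

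**Working it through.** The plan states no figure on this point, so the check is of text, with one labelled illustration.

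1. **Reach of the rule.** SAP 13.1 sends combined PTs to the adverse event tables without exception. The tables it describes cover treatment-emergent events (TEAEs), serious TEAEs (TESAEs), TEAEs leading to permanent discontinuation, and TEAEs of special interest. The 3% and 5% tables in 13.1.1 are adverse event tables too. All carry the mapping.

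2. **What the mapping does to the four terms.**

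| Coded PT | Row in the tables | Other terms in that row |
|---|---|---|
| Pneumocystis jirovecii pneumonia | Pneumonia | Atypical mycobacterial pneumonia; Pneumonia |
| Atypical mycobacterial pneumonia | Pneumonia | Pneumocystis jirovecii pneumonia; Pneumonia |
| Aspergillus infection | Fungal infection | Eight, including onychomycosis and vulvovaginal candidiasis |
| Ventricular tachycardia | Tachycardia | Sinus tachycardia; supraventricular tachycardia; tachycardia |

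3. **Whether another table shows them.** No opportunistic infection grouping is defined. The ECG tables (13.6, 13.7) classify findings only as normal or abnormal, with clinical significance, so they do not identify ventricular tachycardia. For PML, 13.1.5 relies on its own PT row in the TEAE summary in place of a separate table. Appendix 5 closes that route for the four terms.

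4. **Whether a combined row can be unpicked.** The counting rule in SAP 13.1 counts a patient once at each level of summary, at the most severe event. The intensity split shows the grade of that event but not which PT it was. Event totals are also displayed, but again for the combined term.

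5. **Whether the listings fill the gap.** They keep coded PTs, by treatment group, with verbatim term, grade and seriousness (13.1). Serious events (13.1.3), discontinuations (13.1.4) and infections (13.1.5) have further listings. Counts by arm can be rebuilt from these, but no such count is planned.

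6. **Illustration within one row.** The counts are assumed, the arm size is the planned 87 (SAP 5.2), and each patient has one event.
   - Pneumocystis alone: 3/87 = 3.4% v 0/87 = 0%; Fisher p = 0.25.
   - The combined Pneumonia row containing those cases: 6/87 = 6.9% v 5/87 = 5.7%; Fisher p = 1.00.

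   Neither p-value is notable, and the SAP describes no test of adverse event rates. The difference lies in what the reader can see.

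7. **How many cases to expect.** At an assumed true rate r, the chance of at least one case in an arm is 1 − (1 − r)^87. That is 35% at r = 0.5%, 58% at 1% and 83% at 2%. Such events would be few, so hand counting is feasible and separate rows would add little length.

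**The case against.** The strongest reply is that nothing is lost. The listings hold every coded term by arm, and a handful of cases can be counted. This stands, and it rules out a reading that a reader might infer, namely that these events cannot be compared between arms. They can; what is missing is a planned tabulation.

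The second reply is that the layout already limits dilution. Tables are broken down by intensity, so a severe Aspergillus infection is counted at its own grade and not among mild nail infections. Non-serious events do not enter the TESAE table. This also stands for severe and serious events. Dilution remains mainly in the any-grade TEAE and infection rows, and even a severe event is not identified by diagnosis.

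The third reply is that the main safety concerns stay visible. PML is in no Appendix 5 row, and infusion-related reactions and infections overall keep their own summaries. A reader might infer that Appendix 5 hides the events that matter most for a B-cell-depleting drug. The documents do not support that: only a few infection terms are affected, and nothing links ventricular tachycardia to B-cell depletion. It is here only as an example of mixed seriousness. Nor does exclusion criterion 6 ("Patient has a severe infection, such as sepsis, abscesses, active tuberculosis (TB), or opportunistic infections") create a reporting class. It is an eligibility rule that gives opportunistic infections as one example of severe infection.

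Finally, grouping related terms is a legitimate prespecified choice and can gather a signal scattered across PTs. That is fair for herpes zoster, which shares a virus family with the rest of its row. It is less convincing for Aspergillus infection with onychomycosis, or ventricular with sinus tachycardia.

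**Conclusion.** The point holds as a gap in presentation. Four clinically distinct PTs have no row of their own in any adverse event table described in the SAP, and arm-level counts would have to be rebuilt by hand from listings. A rare imbalance can be diluted in the any-grade TEAE and infection rows, less so where severity or seriousness separates the events. The real size is unknown, because the documents give no rates for these events; the 6 v 5 row hiding 3 v 0 is an assumed example.

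The conclusion rests on the SAP text. The table shells are a separate addendum (SAP 2) that was not available here; if they already include tables by coded PT, the point falls away. No data, primary analysis or decision rule is affected. It is a cheap improvement worth making.

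**What to change.** Either of two changes is enough.

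- **Un-map the terms.** Remove Pneumocystis jirovecii pneumonia, atypical mycobacterial pneumonia, Aspergillus infection and ventricular tachycardia from the Appendix 5 groupings, so that each has its own row. The Pneumonia row then holds only itself and can be deleted; Fungal infection keeps eight terms and Tachycardia three.
- **Add coded-term tables.** Keep Appendix 5, but also produce the infection TEAE and TESAE tables by coded PT. Give ventricular tachycardia its own row as well, because the infection table would not contain it and the TESAE table would show it only when serious. This route keeps the broader totals alongside the coded terms.

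Separating herpes zoster is optional. Record the change before the safety tables are run by arm, so that the choice of terms cannot be read as driven by the results. The cost is a few more table rows, or two reruns without the mapping plus one extra row. No data collection, endpoint or sample size changes.
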